7.1.5.2. Incomplete Dates

If the onset date of the AE is incomplete and the AE stop date is not prior to the first dosing date of study drug, then the month and year (or year alone if month is not recorded) of onset determine whether an AE is treatment emergent. The event is considered treatment emergent if both of the following 2 criteria are met:

- The AE onset is the same as or after the month and year (or year) of the first dosing date of study drug, and
- The AE onset date is the same as or before the month and year (or year) of the date corresponding to 30 days after the date of the last dose of study drug

An AE with completely missing onset and stop dates, or with the onset date missing and a stop date later than the first dosing date of study drug, will be considered to be treatment emergent. In addition, an AE with the onset date missing and incomplete stop date with the same or later month and year (or year alone if month is not recorded) as the first dosing date of study drug will be considered treatment emergent.

In case when the AE onset date is incomplete and needs to be imputed, the following algorithm will be followed:

- If the day is missing but the month and year are available, then the imputed day will be the first day of the month or the first dosing date if they have the same month and year, whichever is later.
- If the day and month are missing but year is available, then the imputed day and month will be 01Jan or the first dosing date if they have the same year, whichever is later.

7.1.6. Summaries of Adverse Events and Deaths

Treatment-emergent AEs will be summarized based on the Safety Analysis Set.

7.1.6.1. Summaries of AE Incidence by Severity Grades

The number and percentage of subjects who experienced at least 1 TEAE will be provided and summarized by SOC, HLT PT, and treatment group. For other AEs described below, summaries will be provided by SOC, PT, and treatment group:

- TEAEs
- TEAEs with Grade 3 or higher
- TEAEs related to GS-5829
- TE SAEs

- TE SAEs related to GS-5829
- TEAEs leading to premature discontinuation of GS-5829
- TEAEs leading to death
- TEAEs leading to temporary interruption of GS-5829
- TEAEs leading to dose reduction of GS-5829

A brief, high-level summary of AEs described above will be provided by treatment group and by the number and percentage of subjects who experienced the above AEs.

Multiple events will be counted only once per subject in each summary. Adverse events will be summarized and listed first in alphabetic order of SOC and HLT within each SOC (if applicable), and then by PT in descending order of total frequency within each SOC. For summaries by severity grade, the most severe grade will be used for those AEs that occurred more than once in an individual subject during the study.

In addition to the above summary tables, all TEAEs and TE SAEs will be summarized by PT only, in descending order of total frequency. All TEAEs and TEAEs related to GS-5829 will be summarized by SOC, PT and severity.

In addition, data listings will be provided for the following:

- All AEs, indicating whether the event is treatment emergent
- All AEs with Grade 3 or higher
- All SAEs
- All deaths
- All AEs leading to death
- AEs leading to premature discontinuation of GS-5829
- AEs leading to temporary interruption of GS-5829
- AEs leading to dose reduction of GS-5829

7.1.6.2. Summary of Deaths

A summary (number and percentage of subjects) of deaths will be provided by treatment group. Summary will include the following categories:

- All deaths
- Deaths within 30 days of the last dosing of study drug
- Deaths beyond 30 days of the last dosing of study drug

7.1.7. Additional Analysis of Adverse Events

7.1.7.1. Dose Limiting Toxicity

A listing of the DLT AEs will be provided following the standard AE listing format.

7.1.7.2. Treatment-Emergent Adverse Events (TEAE) of Interest

The following AEs of interest defined by the medical search term (MST) provided by Gilead Pharmacovigilance and Epidemiology (PVE) Department will be summarized similarly to TEAEs by treatment group.

- Decreased Platelets
- Diarrhoea
- Haemorrhage

7.2. Laboratory Evaluations

Laboratory data collected during the study will be analyzed and summarized using both quantitative and qualitative methods. Summaries of laboratory data will be provided for the Safety Analysis Set and will include data collected up to the last dose of study drug plus 30 days for subjects who have permanently discontinued study drug. The analysis will be based on values reported in conventional units. When values are below the LOQ, they will be listed as such, and the closest imputed value will be used for the purpose of calculating summary statistics as specified in Section 3.7. Hemolized test results will not be included in the analysis, but they will be listed in by-subject laboratory listings.

A by-subject listing for laboratory test results will be provided by subject ID number and visit in chronological order for hematology, serum chemistry, coagulation and urinalysis separately. Values falling outside of the relevant reference range and/or having a severity grade of 1 or higher on the CTCAE severity grade will be flagged in the data listings, as appropriate.

7.2.1. Summaries of Numeric Laboratory Results

Descriptive statistics will be provided by treatment group for each laboratory test specified in the study protocol as follows:

- Baseline values
- Values at each postbaseline visit
- Change and percentage change from baseline at each postbaseline visit

A baseline laboratory value will be defined as the last measurement obtained on or prior to the date/time of first dose of study drug. Change from baseline to a postbaseline visit will be defined as the visit value minus the baseline value. The mean, median, Q1, Q3, minimum, and maximum values will be displayed to the reported number of digits; StD values will be displayed to the reported number of digits plus 1.

In the case of multiple values in an analysis window, data will be selected for analysis as described in Section 3.8.3. In the event that both central and local lab results are collected in the clinical database, only central lab results will be included in the summary by visits. All central and local laboratory values will be listed.

7.2.2. Graded Laboratory Values

The CTCAE Version 4.03 will be used for assigning toxicity grades (0 to 4) to laboratory results for analysis. Grade 0 includes all values that do not meet the criteria for an abnormality of at least Grade 1. For laboratory tests with criteria for both increased and decreased levels, analyses for each direction (ie, increased, decreased) will be presented separately. Local labs will be graded based on central lab normal ranges with in-house macro. In the event that both central and local lab results are collected in the clinical database, the worst toxicity grade will be used for the summary of lab toxicities. All central and local laboratory values will be listed.

7.2.2.1. Treatment-Emergent Laboratory Abnormalities

Treatment-emergent laboratory abnormalities are defined as values that increase at least 1 toxicity grade from baseline at any postbaseline time point, up to and including the date of last dose of study drug plus 30 days for subjects who permanently discontinued study drug. If the relevant baseline laboratory value is missing, any abnormality of at least Grade 1 observed within the time frame specified above will be considered treatment emergent.

7.2.2.2. Summaries of Laboratory Abnormalities

Laboratory data that are categorical will be summarized using the number and percentage of subjects in the study with the given response at baseline and each scheduled postbaseline visit.

The following summaries (number and percentage of subjects) for treatment-emergent laboratory abnormalities will be provided by lab test and treatment group; subjects will be categorized according to the most severe postbaseline abnormality grade for a given lab test:

- Baseline grade (Grade 0 to 4 separately, Grade 3 or 4, and Grade 1 to 4)
- Worst treatment-emergent laboratory abnormalities postbaseline grade (Grade 1 to 4 separately, Grade 3 or 4, and Grade 1 to 4)

For all summaries of laboratory abnormalities, the denominator is the number of subjects with nonmissing postbaseline values up to 30 days after the last dosing date.

7.2.3. Liver-related Laboratory Evaluations

Liver-related abnormalities after initial study drug dosing will be examined and summarized using the number and percentage of subjects who were reported to have the following laboratory test values for postbaseline measurements:

- Aspartate aminotransferase (AST): (a) > 3 times of the upper limit of reference range (ULN); (b) $> 5 \times$ ULN; (c) $> 10 \times$ ULN; (d) $> 20 \times$ ULN
- Alanine aminotransferase (ALT): (a) $> 3 \times$ ULN; (b) $> 5 \times$ ULN; (c) $> 10 \times$ ULN; (d) $> 20 \times$ ULN
- AST or ALT: (a) $> 3 \times$ ULN; (b) $> 5 \times$ ULN; (c) $> 10 \times$ ULN; (d) $> 20 \times$ ULN
- Total bilirubin: (a) $> 1 \times$ ULN ; (b) $> 2 \times$ ULN
- Alkaline phosphatase (ALP) $> 1.5 \times$ ULN
- AST or ALT $> 3 \times$ ULN and total bilirubin: (a) $> 1.5 \times$ ULN; (b) $> 2 \times$ ULN
- AST or ALT $> 3 \times$ ULN and total bilirubin $> 2 \times$ ULN and ALP $< 2 \times$ ULN

The summary will include data from all postbaseline visits up to 30 days after the last dose of study drug. For individual laboratory tests, subjects will be counted once based on the most severe postbaseline values. For both the composite endpoint of AST or ALT and total bilirubin, subjects will be counted once when the criteria are met at the same postbaseline visit date. The denominator is the number of subjects in the Safety Analysis Set who have nonmissing postbaseline values of all relevant tests at the same postbaseline visit date. A listing of subjects who met at least 1 of the above criteria will be provided.

7.2.4. Shifts Relative to the Baseline Value

Shift tables will be presented by showing change in severity grade from baseline to the worst postbaseline grade.

7.3. Vital Signs

Descriptive statistics will be provided by treatment group for vital signs as follows:

- Baseline value
- Values at each postbaseline visit
- Change from baseline at each postbaseline visit

A baseline value will be defined as the last available value collected on or prior to the date/time of first dose of study drug. Change from baseline to a postbaseline visit will be defined as the postbaseline value minus the baseline value. Vital signs measured at unscheduled visits will be included for the baseline value selection.

In the case of multiple values in an analysis window, data will be selected for analysis as described in Section 3.8.3.

A by-subject listing of vital signs will be provided by subject ID number and visit in chronological order. High or low values for vital signs will be flagged.

7.4. Prior and Concomitant Medications

Medications collected at screening and during the study will be coded using the current version of the World Health Organization (WHO) Drug dictionary.

7.4.1. Prior Medications

Prior medications are defined as any medications taken before a subject took the first study drug.

A summary of general prior medications will not be provided. Prior medications will be included in a listing together with concomitant medications.

7.4.2. Concomitant Medications

Concomitant medications are defined as medications taken while a subject took study drug. Use of concomitant medications will be summarized by preferred name using the number and percentage of subjects for each treatment group. A subject reporting the same medication more than once will be counted only once when calculating the number and percentage of subjects who received that medication. The summary will be ordered by preferred term in descending overall frequency. For drugs with the same frequency, sorting will be done alphabetically.

For the purposes of analysis, any medications with a start date prior to or on the first dosing date of study drug and continued to be taken after the first dosing date, or started after the first dosing date but prior to or on the last dosing date of study drug will be considered concomitant medications. Medications started and stopped on the same day as the first dosing date or the last dosing date of study drug will also be considered concomitant. Medications with a stop date prior to the date of first dosing date of study drug or a start date after the last dosing date of study drug will be excluded from the concomitant medication summary. If a partial stop date is entered, any medication with the month and year (if day is missing) or year (if day and month are missing) prior to the date of first study drug administration will be excluded from the concomitant medication summary. If a partial start date is entered, any medication with the month and year (if day is missing) or year (if day and month are missing) after the study drug stop date will be excluded from the concomitant medication summary. Medications with completely missing start and stop dates will be included in the concomitant medication summary, unless otherwise specified. Summaries will be based on the Safety Analysis Set.

All prior and concomitant medications (other than per-protocol study drugs) will be provided in a by-subject listing sorted by subject ID number and administration date in chronological order.

7.5. **Electrocardiogram Results**

Electrocardiogram (ECG) analysis results are intended to identify meaningful changes in the QT interval. If potential abnormalities of interest are identified, further analyses may be conducted. Summaries of ECG data will be provided for the Safety Analysis Set for each scheduled time point based on central ECG results. The local ECG assessment results will be used in the data summary if only local ECG measurements are available at a visit/time point. No formal statistical testing is planned.

A by-subject listing for ECG assessment results will be provided by subject ID number and visit in chronological order.

7.5.1. **Corrected QT Intervals**

The QT interval (measured in millisecond [msec]) is a measure of the time between the start of the Q wave and the end of the T wave in the heart's electrical cycle. The QT interval represents electrical depolarization and repolarization of the ventricles. The QT interval is affected by heart rate, and a number of methods have been proposed to correct QT for heart rate.

Corrected QT (QTc) intervals will be derived using Fridericia's correction (QTcF) as follows:

$$QTcF = \frac{QT}{\sqrt[3]{RR}}$$

where QT is measured in msec; RR = 60/Heart Rate (beats per min [bpm]) and RR is measured in seconds

The maximum postdose QTcF interval values obtained during the study will be summarized within the following categories:

- > 450 msec
- > 480 msec
- > 500 msec

The maximum postdose change in QTcF interval values obtained during the study will also be summarized within the following categories:

- > 30 msec
- > 60 msec

QTcF and uncorrected QT values at each visit and time point and change from baseline at each visit and time point will be summarized for the Safety Analysis Set by treatment group using descriptive statistics.

7.5.2. PR and QRS Intervals

The PR interval (measured in msec) is a measure of the time between the start of the P wave (the onset of atrial depolarization) and the beginning of the QRS complex (the onset of ventricular depolarization). The QRS interval measures the duration of the QRS complex. The maximum ventricular rate (VR) and PR and QRS intervals observed during the study will be categorized. The number and percentage of subjects having values in the following ranges will be presented by treatment group:

- VR > 100 bpm
- PR interval > 200 msec
- QRS interval > 110 msec

In addition, VR, PR, RR, and QRS values at each visit and time point and change from baseline at each visit will be summarized for the Safety Analysis Set by treatment group using descriptive statistics.

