- 10) History of a concurrent or second malignancy, except for: adequately treated local basal cell or squamous cell carcinoma of the skin; cervical carcinoma in situ; superficial bladder cancer; breast carcinoma in situ; adequately treated Stage 1 or 2 cancer currently in complete remission; any other cancer that has been in complete remission for  $\geq 5$  years
- 11) History of long QT syndrome or whose corrected QT interval (QTc) measured (Fridericia method) at screening is prolonged ( $> 450$  ms). Subjects who screen fail due to this criterion are not eligible to be re-screened
- 12) Prior exposure to bromodomain (BET) inhibitors
- 13) Clinically significant bleeding within 28 days of Cycle 1 Day 1
- 14) Known human immunodeficiency virus (HIV) infection
- 15) HBsAg positive
- 16) HCV antibody positive
- 17) Use of moderate/strong cytochrome P450 (CYP)3A4 inhibitors or moderate/strong CYP3A4 inducers within 2 weeks prior to the first dose of study drug (with the exception of enzalutamide in the combination arms)

---

- 18) Evidence of bleeding diathesis
- 19) History of hemoptysis of  $\geq 2.5$  mL/1 teaspoon within 6 months of Cycle 1 Day 1
- 20) History of high grade esophageal or gastric varices
- 21) Anticoagulation/antiplatelet therapy within 7 days of Cycle 1 Day 1, including low molecular weight heparin, or warfarin.

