### **8.6. Safety Analysis**

All safety data collected on or after the date that study drug was first dispensed up to the date of last dose of study drug plus 30 days will be summarized by dose level. Data for the pretreatment will be included in data listings.

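### The PR, QRS and ventricular-rate counts in SAP 7.5.2 have no postdose limit and no baseline condition, so they cannot separate new from pre-existing abnormalities

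*SAP*

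**What the plan says.** SAP 7.5.2 gives the rule for three ECG measures: "The maximum ventricular rate (VR) and PR and QRS intervals observed during the study will be categorized". It continues: "The number and percentage of subjects having values in the following ranges will be presented by treatment group". The ranges are VR above 100 bpm, PR above 200 msec and QRS above 110 msec.

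SAP 7.5.1 words the QTcF rule differently: "The maximum postdose QTcF interval values obtained during the study will be summarized within the following categories". It adds categories of change, above 30 and above 60 msec: "The maximum postdose change in QTcF interval values obtained during the study will also be summarized within the following categories". VR, PR and QRS have no such change categories.

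Three other provisions bear on the point:

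- Within 7.5.2: "In addition, VR, PR, RR, and QRS values at each visit and time point and change from baseline at each visit will be summarized".
- In the introduction to SAP 7.5: "A by-subject listing for ECG assessment results will be provided by subject ID number and visit in chronological order".
- Protocol 8.6 opens the window for safety summaries with "All safety data collected on or after the date that study drug was first dispensed", closes it 30 days after the last dose, and sends pretreatment data to listings. SAP 7.8 declares no departure from the protocol's safety analyses.

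The only ECG interval limited at entry is QTc, in Protocol 4.3, criterion 11: "History of long QT syndrome or whose corrected QT interval (QTc) measured (Fridericia method) at screening is prolonged" (above 450 ms). No limit on PR, QRS or heart rate is listed.

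**The concern.** An outlier count is most useful in a dose-escalation study if it shows which subjects crossed a limit after dosing. As written, 7.5.2 does not ask that question. It asks whether a subject was above the limit on any tracing, and it ignores where the subject started. A man who enrols with a long PR or a wide QRS, which the eligibility criteria allow, is counted whether or not the drug does anything.

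The SAP is more careful elsewhere. Treatment-emergent adverse events are dated from the start of study drug (7.1.5.1). Laboratory abnormalities must worsen by at least one grade from baseline (7.2.2.1), with the baseline grade tabulated beside them (7.2.2.2) and a shift table (7.2.4). Liver criteria use postbaseline values (7.2.3). The VR, PR and QRS counts have no counterpart to any of these.

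What is at stake is how readable one descriptive table is. In cohorts of 3 to 6, one subject moves the reported percentage a long way.

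**Working it through.** The documents give no figure that depends on this rule, so there is nothing to reproduce. The check has three steps.

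**Step 1: which tracings can enter the maximum.** Scheduled Phase 1b ECG time points come from footnote 4 of Protocol Appendix 2 and the matching ECG note of Appendix 3, counted through Cycle 6 plus end of treatment.

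- Monotherapy, before any study drug: screening and C1D1 pre-dose = 2.
- Monotherapy, after the first dose: C1D1 post-dose 1 + C1D8 7 + Day 1 of Cycles 2–6 5 + EOT 1 = 14.
- Combination, before any study drug: screening = 1.
- Combination, after enzalutamide but before GS-5829: C1D1 pre-dose = 1.
- Combination, after the first GS-5829 dose: C1D1 6 + C1D15 7 + Day 1 of Cycles 2–6 5 + EOT 1 = 19.

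Read alone, 7.5.2 takes in all of these. SAP 3.8.2 sets only a late cut-off for summaries. Under the Protocol 8.6 window, screening ECGs taken before dispensing drop out. The window is set by date and not by dose time, so the monotherapy C1D1 pre-dose ECG stays in if drug is first dispensed that day. The combination C1D1 pre-dose ECG is already after the first study drug, because SAP 3.1.2 defines study drug as either agent.

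**Step 2: what each correction would achieve.** For a given limit there are four patterns:

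| Baseline | Postdose maximum | Counted by 7.5.2? | Counted with a postdose limit only? | New since baseline? |
|---|---|---|---|---|
| at or below | at or below | no | no | no |
| at or below | above | yes | yes | yes |
| above | above | yes | yes | no |
| above | at or below | yes, if the pre-dose tracing is included | no | no |

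A postdose limit settles only the last row. The third row, a persistent abnormality, is counted under any window. Only a baseline condition separates it from the second row.

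**Step 3: size.** Cohorts are 3 to 6 subjects (SAP 1.2), and Protocol 8.6 summarizes safety by dose level. One pre-existing case therefore shows as 1/3 = 33% or 1/6 = 17%. The chance that a cohort of n holds at least one is 1 − (1 − p)^n, where p is the proportion above a given limit at entry. The documents do not give p, so the values below are assumptions:

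| Assumed p | n = 3 | n = 6 | Expected among 72 (72 × p) |
|---|---|---|---|
| 5% | 1 − 0.95³ = 14.3% | 1 − 0.95⁶ = 26.5% | 3.6 |
| 10% | 1 − 0.90³ = 27.1% | 1 − 0.90⁶ = 46.9% | 7.2 |
| 20% | 1 − 0.80³ = 48.8% | 1 − 0.80⁶ = 73.8% | 14.4 |

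**The case against.** A reader might infer that the SAP reports pre-treatment abnormalities as on-treatment findings. The documents do not support that. Protocol 8.6 confines safety summaries to data from first dispensing onward, SAP 7.8 says the protocol is followed, and nothing in 7.5.2 labels the counts on-treatment or treatment-emergent. For screening ECGs the fault is silence in 7.5.2. It is not an instruction to include them.

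A reader might also infer that the plan gives no way to tell new from old, or that separating the two is the table's stated task. Neither follows. The by-subject chronological listing lets someone identify a pre-existing long PR or wide QRS, which is practical in cohorts this small. The stated aim of the ECG analysis in SAP 7.5 is to find meaningful QT changes, with further analyses possible if something of interest appears.

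The contrast with QTcF is only partial. Its absolute categories have no baseline condition either, although the entry limit and the change categories offset much of that.

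The prevalence range is assumed, and the exclusions for significant disorders, uncontrolled arrhythmia and recent cardiac events (Protocol 4.3, criteria 1, 3 and 5) may lower it.

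All of this stands, and it narrows the point without removing it. The by-visit change from baseline is a group summary and does not show which outliers are new. The listing requires the reader to rebuild the count by hand. Neither makes the tabulated percentage interpretable alone.

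**Conclusion.** The point holds as a limited one. SAP 7.5.2 lacks both the postdose limit used in 7.5.1 and any baseline condition, so its counts cannot separate pre-existing from new abnormalities. For pre-treatment tracings, what remains is an unstated exclusion of screening ECGs and the monotherapy C1D1 pre-dose ECG. The larger part is the missing baseline condition, which no choice of window repairs.

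Each affected subject adds 33 percentage points in a cohort of 3 or 17 in a cohort of 6. The probabilities of 14% to 74% are illustrations under an assumed prevalence of 5% to 20% and are not estimates for this trial.

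The consequence is confined to descriptive safety tables. It would be wrong to infer that dose-finding or efficacy conclusions are at risk: no formal test is planned (SAP 3.5), and no DLT or MTD rule uses this table.

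**What to change.** In SAP 7.5.2:

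1. Define the quantity as the maximum postdose VR, PR and QRS.
2. State whether dose means the first dose of any study drug or the first dose of GS-5829 in the combination groups. This decides how their C1D1 pre-dose ECG is treated.
3. Show each threshold by baseline category (at or below, above). Report subjects new since baseline separately from those already above at baseline.
4. Name the baseline tracing. SAP 3.8.3 defines baseline by date, and monotherapy has pre-dose and post-dose ECGs on the same date.

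The cost is a few words of SAP text and a slightly larger table shell. No new data are needed. If the SAP is already final, SAP section 1 allows the change to be documented in the CSR.
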